**Postoperative ultrasound follow-up:**

- ultrasound assessment of the vascular patch: patch patency, morphology, integrity, complications, and blood flow dynamics.
- detection of complication: thrombosis, dissection, restenosis, infection, fluid collection, pseudoaneurysm formation, fraying or irregularities in patch material
- repeat ultrasound assessment: morphological changes in the vascular patch, evolution of blood flow dynamics, signs of restenosis or complications
- Data obtained from duplex ultrasound: wall thickness, presence of plaque, lumen diameter, peak systolic velocity (PSV), end-diastolic velocity (EDV), mean flow velocity (MFV), pulsatility index (PI), direction of blood flow, velocities, degree of stenosis

## 5. Study Intervention

N/A. Retrospective chart review of standard-of-care exams.

## 6. Drugs, Biologics, Devices

N/A

## 7. Collaborative / Multi-site Research

N/A – Investigator Initiated Project

**PROTOCOL TITLE: *Ultrasound Evaluation for Baxter VASCU-GUARD Vascular Patches Post-Endarterectomy and Complications Assessment***

## **8. Data Privacy / Confidentiality**

Required for all protocol types including Sponsored trials. Provide local information.

The data will be abstracted from Houston Methodist Hospital electronic medical records by the PI and trained members of his research staff. The required information will be transferred from electronic medical records by the research staff to the study specific data collection forms.

Study data will be registered into an electronic, password protected database located on the TMHS server accessible only by the research team, applicable regulatory personnel and authorities.

Documents requiring an investigator's signature, should any be created, will be promptly signed, and dated in real-time. In accordance with departmental policies, research-specific documents will be retained on-site for 6 years post-study closure.

No images, video recordings, or photographs of patients will be requested for this study. Study will remain minimal risk with provisions to limit the risk of loss of confidentiality, outlined in section 17. Minimal PHI identifiers will be utilized to build the cohort. Identifiers will not be utilized for cohort analysis. Sufficient security and data privacy measures will be implemented in terms of data collection, processing, storing, and maintaining the database as per the institutional policies and the regulations of the Health Insurance Portability and Accountability Act of 1996 (HIPAA). Study site/investigators will not disclose any proprietary information or confidential data.

As applicable, the IRB, FDA, or other relevant health authorities will have the right to review study data at any point in time.

Identifier (or parts of)	Recorded	Disclosed	Comment
Names	Yes	No	This information will be gathered for the chart review and will not be provided or shared with anyone not part of the research team or outside of the institution. Only for the purpose for screening patients of inclusion in cohort.
All elements of dates (except year) for dates directly related to an individual, including birth date, admission date, discharge date, date of death; and all	Yes	No	This information will be gathered for the chart review and will not be provided or shared with anyone not part of the research team or outside

**PROTOCOL TITLE: *Ultrasound Evaluation for Baxter VASCU-GUARD Vascular Patches Post-Endarterectomy and Complications Assessment***

ages over 89 and elements of dates (including year) indicative of such age			of the institution. Only for the purpose for screening patients of inclusion in cohort.
Medical record numbers	Yes	No	This information will be gathered for the chart review and will not be provided or shared with anyone not part of the research team or outside of the institution. Only for the purpose for screening patients of inclusion in cohort.

## 9. Data and Specimen Banking

De-identified data pertaining to this investigation will be maintained in encrypted, Houston Methodist provided computers. Only IRB approved study personnel on this study will have access to the study information.

## 10. Study Population

The study population is patients undergoing carotid endarterectomy (CEA) with the use of Baxter VASCU-GUARD vascular patches in all campuses of the Houston Methodist Hospital.

Inclusion criteria:

- Patients aged 18 years and above.
- Patients undergoing carotid endarterectomy with the use of VASCU-GUARD vascular patches.
- Follow-up ultrasound assessment available.

Exclusion criteria:

- No postoperative ultrasound assessment is available.

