**The objectives of this study include:**

*Ultrasound evaluation of Baxter VASCU-GUARD vascular patches:*

Retrospective review of ultrasound recordings and ultrasound reports at one-month, 3-months, 6-months and 1-year follow-up after endarterectomy – if available, to evaluate patch patency, morphology, integrity, complications, and blood flow dynamics.

*Complications assessment:*

Analyze complications linked with Baxter Vascular Patches (VASCU-GUARD), including but not limited to thrombosis, stroke, dissection, restenosis, infection, fluid collection, pseudoaneurysm formation, fraying or irregularities in patch material.

*Correlation with Clinical Outcomes:*

Recognize correlations between ultrasound findings and clinical outcomes. This correlation will complement the understanding of how ultrasound monitoring can predict and influence patient prognosis.

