**Data to be collected:**

- Age at surgery, sex, race
- Preoperative risk factors: HTN, DM, TIA, CAD, HLD, previous strokes, previous thromboembolic events, previous surgeries
- Intraoperative data: Type of patch material used, intraoperative complications (if any), MAP, Heart rate, Medications given, Estimated blood loss, Intraoperative antibiotics given, Intraoperative antiplatelet/anticoagulation medication given
- Postoperative outcomes: Stroke/TIA, Postop ICU time, mortality (up to 30 days)
- Follow up neurological evaluation, any symptoms reported by the patient
- Imaging: MRI/CT, MRA, CTA, TCD, vascular duplex ultrasound

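### Entry requires a postoperative ultrasound, so stroke/TIA, 30-day mortality and ICU time, which need no scan, are counted only in scanned patients

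*Protocol*

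**What the plan says.** Protocol Section 10 opens broadly: "The study population is patients undergoing carotid endarterectomy (CEA) with the use of Baxter VASCU-GUARD vascular patches in all campuses". It then narrows this twice. "Follow-up ultrasound assessment available" is an inclusion criterion, and "No postoperative ultrasound assessment is available" is the only exclusion criterion. Neither says how soon after surgery the scan may be taken. Under Statistical Analysis, Section 4 enrols every subject who meets the criteria, up to 500.

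Section 2 has three objectives: ultrasound evaluation, complications and correlation. The complications objective covers events "including but not limited to thrombosis, stroke, dissection, restenosis, infection, fluid collection" and others. Under its ultrasound follow-up heading, Section 4 gives nearly the same list as "detection of complication: thrombosis, dissection, restenosis, infection, fluid collection, pseudoaneurysm formation, fraying or irregularities in patch material". Stroke is no longer in it. Stroke appears instead in the list of data to be collected: "Postoperative outcomes: Stroke/TIA, Postop ICU time, mortality (up to 30 days". A separate item there reads "Follow up neurological evaluation, any symptoms reported by the patient". Thirty-day mortality and ICU time appear only in that data list; no objective names them.

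The protocol nowhere defines a cohort of all patched patients, a separate denominator for clinical outcomes, or a count of patients left out for want of a scan.

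**The concern.** Having a scan is something that happens after surgery, and the events being counted can change the chance of it. A patient who dies or has a disabling stroke before any scan leaves both numerator and denominator. A patient with a non-fatal stroke or TIA may be scanned because of it. The restriction suits endpoints that are read from the scan. For outcomes recorded without one, it replaces the patients who received the patch with those who were later imaged.

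At stake are the absolute rates of stroke/TIA and 30-day death, the description of ICU time, and a reader's ability to judge whether the selection was alike for old and new packaging. A statistical analysis plan cannot repair this, because it cannot analyse patients who were never enrolled or abstracted.

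**Working it through.** **Figure in the plan.** There is none to reproduce. The 500 in Section 4 is a cap, given without event rate, effect size or power. The protocol gives no share of patients scanned either, so every rate below is an assumption.

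**Reading the sections together.** Section 10 requires a scan; Section 4 enrols those who qualify; Sections 2 and 4 analyse or collect stroke/TIA, 30-day mortality and ICU time. It follows that these three outcomes are known only for scanned patients.

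**Formula.** Let t be the true rate in all patched patients, s1 the share of event patients scanned and s0 the share of other patients scanned. Then

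observed rate = t·s1 / (t·s1 + (1 − t)·s0).

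**Stroke/TIA**, t = 2%, s0 = 0.8, so (1 − t)·s0 = 0.784:
- s1 = 0.3: 0.006 / 0.790 = 0.76%
- s1 = 0.8: 0.016 / 0.800 = 2.00%
- s1 = 1.0: 0.020 / 0.804 = 2.49%

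In counts, 500 operated patients with 10 events leave 490 × 0.8 = 392 scanned patients without an event. The scanned set then shows 3/395, 8/400 or 10/402.

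**30-day mortality**, t = 1%, s0 = 0.8, so (1 − t)·s0 = 0.792:
- s1 = 0.25: 0.0025 / 0.7945 = 0.31%
- s1 = 0.5: 0.005 / 0.797 = 0.63%
- s1 = 0.8: 0.008 / 0.800 = 1.00%, no bias

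With s1 = 0.5, the result is 0.72% if 70% of survivors are scanned and 0.56% if 90% are.

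**Old versus new packaging.** The observed odds equal the true odds times s1/s0. If s1/s0 is the same in both groups, it cancels from the odds ratio. Take true rates of 2% and 4% with s1 = 0.3 and s0 = 0.8 in both groups of 500. The true odds ratio is (20/480) / (10/490) = 2.04; among the scanned it is (6/384) / (3/392) = 2.04. The risk ratio barely moves: 1.54% / 0.76%, or (6/390) / (3/395) = 2.03, against 2.00.

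If the ratio differs by group, the comparison moves. With a true 3% in both groups, s0 = 0.9 in both, and s1 = 0.2 (old) against 0.6 (new), the observed rates are 0.006/0.879 = 0.68% and 0.018/0.891 = 2.02%, a false odds ratio of 3.0. Those shares were chosen freely; nothing in the protocol points to them.

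**The case against.** The strongest reply is that this is an ultrasound study. Its title, its stated aim of comparing standard-of-care exams, and two of its three objectives concern imaging, and no section promises a stroke or death rate for everyone who received the patch. This stands in part. The scan requirement is right for the ultrasound endpoints and for the objective to "Recognize correlations between ultrasound findings and clinical outcomes". Mortality and ICU time carry less weight, since no objective names them. But stroke is in the complications objective, and Section 10 itself introduces the population as all patched patients, so the point does not depend on the other two.

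A second reply is that the comparison survives if selection is equal in both groups. The arithmetic above bears this out. A reader might infer that the old-versus-new comparison is biased; the documents do not support that. There is a reason to look. If the closing date of 30 April 2024 limits scans as well as operations, patients operated on late have less time to be scanned, and all of them have new packaging. The protocol does not say whether the date works that way.

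A reader might also infer, because the first follow-up scan named in Section 2 is at one month, that 30-day deaths are excluded by construction. That goes too far. Section 10 sets no earliest scan, so an in-hospital scan may qualify a patient who later dies.

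Finally, counts of unscanned patients are often left to a report. On their own they would be no finding. They matter here because the exclusion is fixed in the eligibility criteria and its effect cannot otherwise be seen.

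**Conclusion.** The concern holds for absolute rates. As written, stroke/TIA, 30-day mortality and ICU time describe scanned patients, not patients who received the patch. Mortality is understated if decedents are scanned less often than survivors. The direction for stroke/TIA is unknown: fatal or disabling strokes may be lost, while non-fatal events may prompt a scan.

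The size cannot be derived from the protocol and may be nil. The illustrations show how far the rates could move under assumed scan shares; they do not estimate how far they do. Distortion of the packaging comparison is possible but unproven, and it cannot be checked without counts of unscanned patients by group. The ultrasound comparison is not affected by this point. The change is worth making because it is cheap and removes the selection from outcomes that do not need it.

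**What to change.** - **Section 10:** define the cohort as all adults with CEA and a VASCU-GUARD patch in the study window. Make at least one postoperative ultrasound the condition for the analysis set used for ultrasound endpoints and the correlation objective only.
- **Clinical outcomes:** analyse stroke/TIA and mortality, both within the same 30-day window, and postoperative ICU time in the full cohort by packaging group. The 30-day limit in the data list follows mortality, and no window for stroke/TIA is clearly stated.
- **Reporting:** give the numbers operated, scanned and not scanned by group.
- **Unknown 30-day status:** show both the stroke/TIA and the mortality rates with unknowns counted as event-free and then as events.
- **Section 4 cap:** apply the maximum of 500 to scanned patients and restate the total number of records under the waiver. If the cap is reached, that is 500/0.9 = 556 to 500/0.7 = 714 operated patients when 90% to 70% are scanned. Left on all patients, the cap would leave 450 to 350 scanned.

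The cost is limited extra abstraction for unscanned patients, who can be identified when records are screened (Section 11), and the restated record count. Status may remain incomplete, because the sources are hospital records, DigiView and office charts, with no death-registry linkage described. For example, assuming 500 operated and 5 recorded deaths, 5 unknowns bound mortality at 5/500 = 1.0% to 10/500 = 2.0%, and 25 unknowns at 1.0% to 30/500 = 6.0%. Wide bounds would be less informative, but they would show the reader what is not known.

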## 11. Screening and Recruitment SR

Subjects will be retrospectively identified through retrospective review of medical records.

## 12. Withdrawal of Subjects

**PROTOCOL TITLE: *Ultrasound Evaluation for Baxter VASCU-GUARD Vascular Patches Post-Endarterectomy and Complications Assessment***

N/A

**13. Provisions to Protect the Privacy Interests of Subjects**

N/A

**14. Risks to Subjects**

This research involves no more than minimal risk because it will involve only a retrospective review of clinical records. All Confidentiality and Data privacy protocols will be strictly adhered to.

**15. Potential Benefits**

Future participants may receive improved care as the outcome data from this study can influence current practices. However, no direct benefits to participants are anticipated from this research.

**16. Financial and Economic Issues**

Investigator Initiated project – Funding source for project currently Baxter International

**17. Data Safety Plan**

The HMRI SOP's will be strictly adhered to in terms of data safety. All information will be kept in excel spreadsheets on locked computers within Houston Methodist Hospital. Information will not be provided outside of the institution. All investigators will be added to the research study via MORTI before assisting in the research study.

**18. Waiver of Informed Consent and /or Authorization**

Requesting a waiver of informed consent and HIPAA waiver of authorization.

We are requesting a waiver of authorization for the conduct of this research study. As this project only involves the analysis of secondary data in the patient chart, it is deemed minimal risk for participants, and therefore, a waiver of consent can apply. All data being collected are

PROTOCOL TITLE: *Ultrasound Evaluation for Baxter VASCU-GUARD Vascular Patches Post-Endarterectomy and Complications Assessment*

part of the standard of care, and thus, a waiver should apply as the data being collected is used to understand underlying factors that affect the variables being collected.

### **Waiver of HIPAA Authorization for Research**

Complete this section if you will access identifiable health information in a patient's electronic health record or other record held by Houston Methodist Hospital and you are not obtaining a signed authorization from the patient. This waiver can apply to health information accessed to identify potential research participants or for research involving retrospective chart reviews.

1. Purpose of the Waiver:

- Chart review study – collecting retrospective clinically available data that will not have bearing on clinical outcomes.
- Partial waiver of authorization to identify, prescreen and contact potential participants.
- Alteration of the requirements for a HIPAA Authorization to remove the signature. \*
- Other Please explain Retrospective Study – clinically available data only

***\* Note if the IRB waives the signature requirement, the participant must receive a copy of the HIPAA authorization language.***

2. Provide protocol-specific responses to the following items that describe why the waiver is being requested for the use of PHI in this research.

a. The IRB must find that the use/disclosure of protected health information (PHI) involves no more than minimal risk to the privacy of individuals. Please select the safeguards your team will use to meet this requirement.

- Electronic safeguards, such as password protection, data encryption, and institution firewall, will be used to protect PHI
- Physical safeguards, such as locked cabinets, locked filing room, secure, locked office area, will be used to protect PHI
- The study team will record only anonymous data or coded data that are linked to the participants' identity through a file that is separate from the data.
- Administrative safeguards such as policies and procedures, staff education on the HIPAA Privacy Rule.

Other: \_\_\_\_\_

c. Describe why the research cannot practically be conducted without the waiver or alteration of patient authorization to use PHI in research

- Access to and use of PHI is necessary to obtain information of potential subjects.
- The number of screen failures is anticipated to be high for this research and access to

**PROTOCOL TITLE: *Ultrasound Evaluation for Baxter VASCU-GUARD Vascular Patches Post-Endarterectomy and Complications Assessment***

the PHI to confirm potential study eligibility will prevent unnecessary contact with potential participants.

Too many participants will be lost to follow up or will not answer the request for an authorization to conduct the record review study.

Other: \_\_\_\_\_ **Retrospective Study – clinically available data only**

d. Describe why the research cannot practically be conducted without access to and use of the PHI:

The study team will access the minimum PHI necessary to contact potential participants to assess their interest and eligibility.

The study team will access the minimum PHI necessary to prescreen for eligibility.

The study team will access the minimal PHI necessary data elements to answer the research question.

**\*Retrospective Chart Review\* PHI only accessed and recorded locally for the purpose of screening patients for inclusion in cohort. Patients will consent to SOC procedures and surgical consents, which state**

3. Identify

List the identifiers you will record by HMRI research team only, not disclosed. Minimal PHI will be accessed

Name

Address (all geographic subdivisions smaller than state, including street address, city county, and zip code)

All elements (except years) of dates related to an individual (including birthdate, admission date, discharge date, date of death, and exact age if over 89)

Telephone number

Fax number

Email addresses

Social Security Number

Medical record number

Health plan beneficiary number

Account number

Certificate or license number

Vehicle identifiers and serial numbers, including license plate numbers

Device identifiers and serial numbers

Web URL

Internet Protocol (IP) Address

Finger or voice print

Photographic image - Photographic images are not limited to images of the face.

Any other characteristic that could uniquely identify the individual

**PROTOCOL TITLE: *Ultrasound Evaluation for Baxter VASCU-GUARD Vascular Patches Post-Endarterectomy and Complications Assessment***

By submitting this request for waiver of patient authorization, I certify:

- (1) That the identifiers will be destroyed at the earliest opportunity consistent with the conduct of the research as defined by federal, state, and/or local laws and regulations.
- (2) The PHI will not be reused or disclosed to any other person or entity, except as required by law, for authorized oversight of the research study, or for other research for which the use or disclosure of PHI would be permitted.

